#### 7.4.1. **PK/PD cohort**

Participants in the PK/PD cohort will be subject to PK sampling during a single month either season over the course of the study. During that month, for enrolled participants, each of the three IVM doses will be directly observed. Small volume capillary blood samples ( $\leq 0.5\text{mL}$ ) will be taken to determine IVM plasma concentration at up to 5 time points following the last dose of IVM. Participants will be visited on days 0 (day of 1st dose of IVM), day 1, and 2 to observe IVM dosing. PK sampling will occur at selected time points on up to 5 additional days (day 2, 3, 4, 7, 14, 21, and 28).

### 7.5. **Final Study Visit**

The active case surveillance final study visit of the intervention phase will occur 30 days following the final IVM MDA in season 2, approximately in November. On this visit, members of the parasitology team or the nurses will take a finger blood sample from all cohort children and a cross-sectional blood sample from subset of enrolled adult participants. Additional follow-up will occur for pregnancy follow-up

### **7.6. Early Termination Visit (if needed)**

No early termination visits will occur if early termination is required or requested by a participant.

### **7.7. Unscheduled Visit (if needed)**

All participants will be encouraged to directly contact their assigned nurse or the field physician regarding any health emergencies or consultations at any time during the intervention phase each rainy season by mobile phone supplied to the CHW stationed in each village. During unscheduled visits, the nurse will record patient information in the CRF and diagnose and treat any simple AEs as able under the consultation of the study physicians and/or refer the participant to the district health clinic or hospital. If a participant is found to meet the case definition of malaria during this visit, a blood smear and filter paper will be collected.

### **7.8. Additional Sampling**

---

**SAMPLES WILL ALSO BE OBTAINED AT ADDITIONAL TIMEPOINTS IN A SUBSET OF PARTICIPANTS--ALL CROSS-SECTIONAL HOUSEHOLDS AND SELECT OTHERS--IN ORDER TO OBTAIN A BASELINE ESTIMATE FOR PREVALENCE ESTIMATES. THESE FINGER PRICK BLOOD SAMPLES WILL BE COLLECTED DURING THE DRY SEASONS IN 2020 AND 2021, DURING THE WET SEASON IN 2021 AND AT UP TO 4 OTHER TIMEPOINTS THROUGHOUT THE YEAR. BLOOD SAMPLES WILL BE DRAWN VIA FINGER PRICK AND WILL BE PRESERVED ON SLIDES AND FILTER PAPERS FOR LATER ANALYSIS. BASELINE SAMPLES WILL ALLOW FOR BETTER ASSESSMENT OF CHANGES OCCURRING WITH IVM AND SMC DRUG PRESSURE. THIS ADDITIONAL SAMPLING WILL UTILIZE A SEPARATE INFORMATION SHEET AND CONSENT DOCUMENT. ONLY PARTICIPANTS WHO CONSENT TO PARTICIPATE IN THE ADDITIONAL SAMPLING WILL DO SO. STUDY PROCEDURES/EVALUATIONS**

#### **7.9. Clinical Evaluations**

Clinical evaluations during active case surveillance will be specific to looking for signs and symptoms of uncomplicated malaria; specifically: 1) fever or history of fever in the previous 24 hours and 2) a positive malaria rapid diagnostic test. Signs and symptoms of complicated (serious) malaria (as listed in Appendix D) will also be assessed. AEs reported to the clinical team will be assessed for their seriousness, intensity, and causality related to the intervention by the field physician. Known common side effects from IVM MDA such as pruritis, dizziness, diarrhea or vomiting will be evaluated and treated according WHO guidelines (Appendix B), and the nurse will consult with the field physician if a full clinical evaluation or referral should be performed.

---

## 7.10. Laboratory Evaluations

### 7.10.1. Clinical Laboratory Evaluations

No pre-specified formal clinical laboratory evaluations will occur during the intervention phase of the trial, other than in the PK/PD cohort. Rather, only field tests with RDTs will be performed, and blood samples taken for later analyses that will occur between the 2 rainy seasons or after the intervention phase. RDTs for parasite infection to diagnose malaria episodes will be used by nurses in the field, as will urine RDTs to determine pregnancy status in women 12-45 years of age (and those not yet reaching menopause) in the week prior to each IVM MDA. Blood smears taken by nurses and the parasitology team will be stored for later staining and counting of asexual parasites and species by trained parasitologists. Blood smears will only be read urgently when advised by the clinical team to rule out severe malaria.

#### 7.10.1.1. PK/PD cohort

Participants in the PK/PD will be subject to capillary PK sampling up to 5 time points from the following sampling times 0 (pre-last dose), 1, 4, 8, 12, 24, 48, 52, 60, 72 hours, and on day 7, 14, 21, and 28. At up to 3 time points, simultaneous capillary and venous samples will be taken to assess the correlation between concentrations in these matrices, enabling us to compare our data with previous studies, and inform our mosquito-based studies. Clinical laboratory safety monitoring (5 mL venous draw) will also be conducted on days 0 (pre-IVM), day 14, and day 28 in all PK/PD participants, which will entail a complete blood count (CBC) with differential, liver enzymes (alanine aminotransferase (ALT) and aspartate aminotransferase (AST)), and creatinine (Cr).

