**Table 3: Summary of the study groups and schedule for blood sampling.**

Group	Number to sample	Ages	What and when samples collected				
			BS=blood smear FP=filter paper	BS&FP -when malaria diagnosed	BS&FP -before season	BS&FP -between the second and third MDA each season	BS&FP -dry season/ post intervention (only from select participants)
Child cohort (followed with active case surveillance)	~1800	≤10 yr. olds	BS&FP -when malaria diagnosed	BS&FP -before season	BS&FP -between the second and third MDA each season	BS&FP -post season	BS&FP -dry season/ post intervention (only from select participants)
Households# on village transects (3 villages/arm; ~8 households/village)	~380	all note: ≤10 yr. olds will be sampled in the ACD cohort		BS&FP -before season	BS&FP -between the second and third MDA each season	BS&FP -post season	BS&FP -dry season/ post intervention
PK-PD modeling cohort	180	5-10yo (n=30 per arm) 11-18yo (n=30 per arm) ≥19yo (n=30 per arm)	Each participant sampled for capillary blood up to 5 of the following time points after their last dose of IVM: 0h (pre-last dose), 1h, 4h*, 8h, 12h*, 24h, 48h, 52h, 60h, 72h, 7d*, 14d, 21d and 28d. *venous blood will be collected simultaneously at these time points				

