### 7.3.1. PK/PD cohort

PK/PD cohort children will be chosen from one control and one intervention village, using the arm code so as not to break the blind. They will be subject to follow-up at an increased frequency. Enrollment criteria are otherwise as for the ACD cohort, with additional exclusion criteria of a 1) hemoglobin <7 g/dL (done by Hemocue or other instrument), and 2) use of concomitant medications (Section 6.6). The total number of participants in the PK/PD cohort is n=180 and participants will be age-stratified. Up to one individual may be enrolled from each age strata within the same household:

- 5-10yo (n=60, 30 from each village-arm)
- 11-18yo (n=60, 30 from each village-arm)
- $\geq 19$ yo (n=60, 30 from each village-arm)

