#### 7.10.1.2. Instructions for Specimen Preparation, Handling, and Storage

Capillary blood from participants will be obtained by study nurses wearing disposable gloves, and by first wiping down the participant's finger using an alcohol wipe, and using a sterile, single-use lancet. Nurses handling patient blood will follow safety guideline SOPs and training for handling potentially-infectious human blood and body fluids. Dried blood spots and blood slide smears will be taken during ACD by study nurses will be labeled with the appropriate date and participant ID, and will be stored in their backpacks and slide cases until they return from the field. Upon return, the nurses will store the blood spots in designated containers at the field station, and fix and stain the blood slides following a SOP to be written by the parasitology team. The stained slides will then be transferred to the parasitology

laboratory monthly by car at the IRSS for subsequent examination and dried blood spots will be stored at -20°C for later molecular analyses.

These participant samples will be retained at the IRSS and/or at laboratories in the U.S or the Netherlands for further tests. Consent for the future use of these coded specimens is written into the ICFs.

Capillary and venous samples taken from the PK-PD cohort will be used to assess the correlation between concentrations in the time and compartment matrices. Samples will be placed on ice and centrifuged, plasma stored at -80°C, and shipped to Yale on dry ice. IVM will be quantified using an Agilent 6550 Quadrupole LC/MS/MS that is coupled in line to an Agilent 1290 Infinity LC system. Blood fed mosquito samples collected from the same participant's house will be similarly frozen individually at -80°C and ship them to CSU for subsequent analysis. The presence of IVM in blood meals will be determined using a derivatization + HPLC-fluorescence method. Additionally, a subset capillary blood spots representing those sleeping in each sampling house, and mosquito blood meals from that house will be profiled using DNA fingerprinting analysis. Data will be analyzed to determine if certain individuals/demographic strata (e.g. age groups and sex) receive more bites than expected over time, and how this relates to their IVM plasma concentration.

Clinical labs (CBC, AST, ALT, and Cr) will be collected in appropriate vacutainers and analyzed at the central IRSS laboratory.

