5. APPENDIX: FUTURE WORK TO BE CONSIDERED

- 1. Pharmacokinetic/dynamic parameters
 - a. Impact of age on IVM PK
 - b. Evaluation of IVM metabolites
 - c. Relationship of IVM PK with blood-feeding results done at CSU
 - d. Safety of IVM (clinical, hematology, chemistry)
 - e. Comparison on capillary and venous measurements of IVM

2. Parasite data

- a. Parasitemia [Count data] done by quantitative PCR compare (log10) distributions in populations between arms
 - i. SMC-treated only
 - ii. IVM/placebo-treated only
 - iii. all cohort
- b. Multiplicity of Infection (MOI) per episode or sampling timepoint and molecular Force of Infection (mFOI) per child [Count data] done by either genotyping microsatellites or amplicon deep sequencing
 - i. Regression analysis with Poisson distribution, in an unadjusted analysis followed by an adjusted analysis taking into account the random effects of the cluster (village) and household and fixed effects such as sex, LLIN use, age, and treatment with SMC or IVM.

3. Entomology data

- a. Survivorship bioassays of blood fed mosquitoes [Survival assays]
 - i. Consider time variable
- b. Catch density [count data]
 - i. Consider time variable
- c. Age structure
 - i. Age distribution of mosquitoes in Intervention vs. Control clusters
 - ii. Proportion of mosquitoes caught over an age cut-off (>10 days)
 - 1. Consider time variable
- d. Proportion of mosquito blood meals taken from humans vs other animals
 - i. Consider time variable
- e. Proportion of mosquitoes with sporozoites
 - i. Consider time variable
- f. Entomological inoculation rates (human biting proportion x sporozoite rate)
 - i. Consider time variable

4. Other studies

- a. Impact of IVM on the prevalence of drug and insecticide resistance
- b. Impact of IVM on all-cause anemia in children
- c. Household survey association of household factors and vector density

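### The protocol relates capillary to venous ivermectin by correlation, which cannot reveal or correct a constant-factor difference that would distort comparisons of absolute levels with previous studies

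*Protocol*

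**What the plan says.** Protocol section 7.10.1.1 plans simultaneous capillary and venous samples at up to three time points. It states: "venous samples will be taken to assess the correlation between concentrations in these matrices, enabling us to compare our data with previous studies", and it also means them to support the mosquito work. Section 7.10.1.2 repeats the method: "Capillary and venous samples taken from the PK-PD cohort will be used to assess the correlation between concentrations in the time and compartment matrices". In the blood sampling schedule (Table 3) the 4 h, 12 h and 7 d times are starred, with the note "venous blood will be collected simultaneously at these time points".

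Section 7.3.1 gives the size: "The total number of participants in the PK/PD cohort is n=180". They come from one control and one intervention village, with 30 per age stratum in each.

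The SAP mentions the matter once, as item 1e of the section 5 appendix on future work: "Comparison on capillary and venous measurements of IVM". It names no method.

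Neither document plans a capillary/venous ratio or difference, limits of agreement, a concordance coefficient, a conversion equation or an acceptance limit. Neither says which correlation coefficient is meant.

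**The concern.** To set this trial's concentrations beside those of earlier studies, the reader must know whether a capillary value of a given size means the same as a venous value of that size, and if not, by what factor they differ. That is a question of agreement, or of calibration. Correlation answers another question: whether participants who are high in one matrix tend to be high in the other. A strong correlation is compatible with capillary levels that are half, equal to, or double the venous levels.

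Capillary samples carry most of the PK work, with up to five capillary times against up to three paired venous times. Protocol section 3.2.2 names Cmax and half-life among the parameters to be estimated from blood. If the matrices differ by a factor, Cmax and exposure from capillary blood differ from their venous counterparts by the same factor. A correlation would give no sign of it.

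**Working it through.** **Plan's own figure.** There is no sample size, power or margin for this comparison to reproduce. The cohort count is consistent: 3 strata × 30 × 2 villages = 180, of whom 3 × 30 = 90 are in the ivermectin village.

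**Step 1. Invariance.** Let V be the venous and C the capillary concentration, and multiply C by a constant k > 0.

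- Raw scale: corr(V, kC) = k·cov(V, C) / (SD(V)·k·SD(C)) = corr(V, C).
- Log scale: log(kC) = log k + log C. This is a shift, which leaves the correlation unchanged.
- Spearman and Kendall: the ranks do not change.

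This is algebra and needs no assumption about the data.

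**Step 2. Illustration.** Assumed inputs, none from the documents: 90 participants with pairs at three times, venous medians of 80, 40 and 3 units, between-participant log SD 0.45, paired-error log SD 0.15. The same data were used with three values of k.

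| k | Pearson, raw | Pearson, log | Spearman | Kendall | Geometric mean ratio (95% limits of agreement) |
|---|---|---|---|---|---|
| 0.5 | 0.9797 | 0.9955 | 0.9860 | 0.9030 | 0.49 (0.37 to 0.65) |
| 1 | 0.9797 | 0.9955 | 0.9860 | 0.9030 | 0.98 (0.75 to 1.29) |
| 2 | 0.9797 | 0.9955 | 0.9860 | 0.9030 | 1.97 (1.49 to 2.58) |

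The size of the coefficients depends on the assumptions; their equality down each column does not. The last column separates the three cases.

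**Step 3. What a constant factor does and does not affect.** If capillary(t) = k × venous(t), then:

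- Cmax and exposure are multiplied by k, so comparison of absolute levels with earlier venous data is off by k.
- log capillary(t) = log k + log venous(t), so the slope over time, and hence half-life, is unchanged.
- In a ratio of two age or sex strata, k cancels.
- Ivermectin in blood meals is measured in the mosquitoes by a separate assay (section 7.10.1.2), so k does not enter.

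If the ratio R(t) is not constant, half-life is also affected. The log slope between 12 h and 7 d (168 h) shifts by log(R(168)/R(12)) / (168 − 12). This is why constancy of the ratio needs checking.

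**Step 4. Can the planned samples estimate the ratio?** With one pair per participant and s the SD of the log ratio, the 95% CI of the geometric mean ratio is ×/÷ exp(t × s/√n), with t on n − 1 degrees of freedom. The documents give no s, so a range is shown.

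| s (assumed) | n = 90 | n = 30 | Limits of agreement, ×/÷ exp(1.96 s) |
|---|---|---|---|
| 0.1 | 1.02 | 1.04 | 1.22 |
| 0.2 | 1.04 | 1.08 | 1.48 |
| 0.3 | 1.07 | 1.12 | 1.80 |
| 0.4 | 1.09 | 1.16 | 2.19 |

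The n = 30 column covers a single age stratum, or a paired time at which only a third of the ivermectin participants are sampled.

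**The case against.** The strongest reply is that the wording sits under laboratory evaluations, as a reason for drawing paired blood, and is not a formal analysis plan. The SAP says comparison, not correlation, and defers the work. Enabling comparison with previous studies may mean bridging: relating one matrix to the other and converting. Bridging does not need a ratio near 1.

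Much of this stands. The SAP leaves room for an agreement analysis, and a ratio far from 1 would do no harm once estimated and applied. But the protocol names correlation in two places and neither document plans the estimate that bridging needs. The PK hypotheses in section 10.1 (change over time, variation by age and sex, detectable drug in blood meals) survive a constant factor, so the reply rightly limits the point to absolute levels.

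A reader might infer more than the documents support:

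- *A test of zero correlation is planned and would always be significant.* No test, null or alpha is stated for this comparison. The two-tailed rule in section 10.4 is written for entomological and parasitological outcomes.
- *The correlation is bound to be very high.* Under assumed CVs of 40% between participants and 20% for error in each matrix (log variances 0.148 and 0.039), r at one time is 0.148/(0.148 + 0.039) = 0.79. Values of 0.93 or more arise when the three times are pooled across the decay curve (0.93 at an assumed half-life of 84 h, higher at shorter ones). No passage says they will be pooled, and participants may not all have three pairs.
- *Placebo pairs at zero would inflate it.* Nothing says that they enter the comparison, and on the log scale they are undefined.
- *A concentration threshold in the mosquito studies would be wrong.* The documents plan no such threshold.

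**Conclusion.** The point holds in a limited form. The method that the protocol names for the paired samples cannot show or correct a systematic difference between capillary and venous levels, yet the protocol presents it as what makes comparison with previous studies possible. The error it could hide equals the capillary/venous factor, whatever that is. The documents give no information on its size, and it may be close to 1.

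Only comparisons of absolute Cmax or exposure with earlier studies are exposed if the factor is constant. The primary malaria outcome is not touched. This is a minor point on a secondary PK objective.

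The conclusion rests on the invariance in step 1 and on reading correlation as one of the usual coefficients. A concordance coefficient would respond to a scale difference (0.65, 0.98 and 0.62 on the raw scale for k = 0.5, 1 and 2 in the simulated data), but nothing suggests that one is meant, and it would not supply a conversion factor.

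**What to change.** In protocol sections 7.10.1.1 and 7.10.1.2, replace correlation by an analysis of agreement on the log scale, and give the same method for SAP appendix item 1e:

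- Use pairs from ivermectin-arm participants with both values above the quantification limit, and report how many pairs are excluded at each time.
- Model the log capillary/venous ratio with paired time as a factor and a random effect for participant. Report the geometric mean ratio with its 95% CI and the 95% limits of agreement at each of 4 h, 12 h and 7 d.
- Check whether the ratio is constant over time and over concentration, using the mean of the two log values as the measure of concentration.
- When capillary values are set beside earlier venous data, apply the estimated ratio (time-specific if it is not constant) and carry its uncertainty into the comparison.

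A correlation may still be reported as description. The change costs a few sentences and a small analysis on samples already planned; step 4 indicates that the cohort is large enough. The downside is that a conversion factor and its uncertainty must be reported with any external comparison.

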#### 7.10.1.2. Instructions for Specimen Preparation, Handling, and Storage

Capillary blood from participants will be obtained by study nurses wearing disposable gloves, and by first wiping down the participant's finger using an alcohol wipe, and using a sterile, single-use lancet. Nurses handling patient blood will follow safety guideline SOPs and training for handling potentially-infectious human blood and body fluids. Dried blood spots and blood slide smears will be taken during ACD by study nurses will be labeled with the appropriate date and participant ID, and will be stored in their backpacks and slide cases until they return from the field. Upon return, the nurses will store the blood spots in designated containers at the field station, and fix and stain the blood slides following a SOP to be written by the parasitology team. The stained slides will then be transferred to the parasitology

laboratory monthly by car at the IRSS for subsequent examination and dried blood spots will be stored at -20°C for later molecular analyses.

These participant samples will be retained at the IRSS and/or at laboratories in the U.S or the Netherlands for further tests. Consent for the future use of these coded specimens is written into the ICFs.

Capillary and venous samples taken from the PK-PD cohort will be used to assess the correlation between concentrations in the time and compartment matrices. Samples will be placed on ice and centrifuged, plasma stored at -80°C, and shipped to Yale on dry ice. IVM will be quantified using an Agilent 6550 Quadrupole LC/MS/MS that is coupled in line to an Agilent 1290 Infinity LC system. Blood fed mosquito samples collected from the same participant's house will be similarly frozen individually at -80°C and ship them to CSU for subsequent analysis. The presence of IVM in blood meals will be determined using a derivatization + HPLC-fluorescence method. Additionally, a subset capillary blood spots representing those sleeping in each sampling house, and mosquito blood meals from that house will be profiled using DNA fingerprinting analysis. Data will be analyzed to determine if certain individuals/demographic strata (e.g. age groups and sex) receive more bites than expected over time, and how this relates to their IVM plasma concentration.

Clinical labs (CBC, AST, ALT, and Cr) will be collected in appropriate vacutainers and analyzed at the central IRSS laboratory.

#### **7.10.1.3. Specimen Shipment**

These samples will be coded according to the participants study ID and time-stamped and signed. They will be maintained and tracked by the study pharmacologist in a specimen-tracking log, including details on tracking shipments from Burkina Faso to the laboratories in the U.S and the Netherlands.

## 8. ASSESSMENT OF SAFETY

### 8.1. Definitions

**Adverse Event (AE):** (ICH) E6 defines an AE as any untoward medical occurrence in a patient or clinical investigation subject administered a pharmaceutical product regardless of its causal relationship to the study treatment. FDA defines an AE as any untoward medical occurrence associated with the use of a drug in humans, whether or not considered drug related.

An AE can therefore be any unfavorable and unintended sign (including an abnormal laboratory finding), symptom, or disease temporally associated with the use of a medicinal (investigational) product. The occurrence of an AE may come to the attention of study personnel during study visits and interviews of a study recipient presenting for medical care, or upon review by a study monitor.

All AEs, will be captured on the appropriate data collection form. Information to be collected for AEs includes event description, date of onset, an assessment of severity, relationship to study product and alternate etiology (assessed only by those with the training and authority to make a diagnosis), date of resolution, seriousness, and outcome. AEs occurring during the trial collection and reporting period will be documented appropriately regardless of relationship. AEs will be followed through resolution.

Any medical condition that is present at the time that the subject is screened will be considered as baseline and not reported as an unsolicited AE. However, if the severity or frequency of any pre-existing medical condition increases, it will be recorded as an unsolicited AE.

If an event meets both the criteria of a study endpoint and an adverse event, the event will be reported either as a study endpoint or as an adverse event (not both).

**Serious Adverse Event (SAE):** An AE is considered “serious” if, in the view of either the site principal investigator or sponsor, it results in any of the following outcomes:

- Death,
- A **life-threatening AE:** An AE is considered “life-threatening” if, in the view of either the site principal investigator or sponsor, its occurrence places the patient or subject at immediate risk of death. It does not include an AE that, had it occurred in a more severe form, might have caused death.
- Inpatient hospitalization or prolongation of existing hospitalization,
- A persistent or significant incapacity or substantial disruption of the ability to conduct normal life functions, or

- A congenital anomaly/birth defect.
- Important medical events that may not result in death, be life-threatening, or require hospitalizations may be considered serious when, based upon appropriate medical judgment they may jeopardize the patient or subject and may require medical or surgical intervention to prevent one of the outcomes listed in this definition. Examples of such medical events include allergic bronchospasm requiring intensive treatment in an emergency room or at home, blood dyscrasias or convulsions that do not result in inpatient hospitalization, or the development of drug dependency or drug abuse.

**Note:** Medical judgment should be exercised in deciding whether an adverse event should be classified as serious in other situations. Important adverse events are not immediately life-threatening or do not result in death or hospitalization, but may jeopardize the subject or may require intervention to prevent one of the other outcomes listed in the definition above, should also be considered serious.

